### Schedule of Activities for Patients with Follicular Lymphoma: Dose-Escalation and Expansion Phases (cont.)

---

- x Refer to [Appendix 3](#) for detailed schedule.
- y Includes circulating lymphoma cells and/or cell-free circulating-tumor DNA.
- z Includes B-cell counts (CD19), T-cell counts (CD3, CD4, and CD8), and natural killer cell counts (CD16 and CD56).
- aa Requires separate patient consent for RBR participation. Not applicable for a site that has not been granted approval for RBR sampling.
- bb Availability of adequate archival or freshly biopsied tumor tissue samples should be confirmed at screening (see Section [4.5.6](#) for details).
- cc A tumor biopsy sample is preferred and recommended at the time of progression unless no adequate tumor site is accessible.
- dd After informed consent has been obtained but prior to initiation of study treatment, only serious adverse events caused by a protocol-mandated intervention should be reported. After initiation of study treatment, all adverse events will be reported until 90 days after the last dose of study treatment. After this period, the Sponsor should be notified if the investigator becomes aware of any serious adverse event that is believed to be related to prior study treatment (see Section [5.6](#)). An exception is made for Grade 3 and 4 infections (related and unrelated) in patients who received obinutuzumab, which should be reported until up to 2 years after the last dose of study treatment. The investigator should follow each adverse event until the event has resolved to baseline grade or better, the event is assessed as stable by the investigator, the patient is lost to follow-up, or the patient withdraws consent. Every effort should be made to follow all serious adverse events considered to be related to any of the study treatment components or trial-related procedures until a final outcome can be reported.
- ee The screening PET-CT scan must be performed within 35 days prior to Day 1 of Cycle 1.
- ff Perform only for patients who receive at least two cycles of induction treatment.
- gg If PET-CT scan is positive at the EOI, perform 12 months after initiation of induction treatment, within 14 days prior to study treatment administration.
- hh CT scan of the neck (if clinically indicated), chest, abdomen and pelvis. If contrast is medically contraindicated (e.g., patients with contrast allergy or impaired renal clearance), MRI scans of the chest, abdomen, and pelvis (and neck, if clinically indicated) and a non-contrast CT scan of the chest may be performed. Combined PET/CT scanners may be used to collect diagnostic CT scans but only according to the technical guidelines in the imaging manual. Screening CT scan must be performed within 35 days prior to Day 1 of Cycle 1.
- ii Perform within 7 days prior to Day 1 of Cycle 3.
- jj Perform 12, 18, and 24 months after initiation of induction treatment, within 14 days prior to treatment administration.
- kk Perform only if not done within the previous 3 months.
- ll Perform every 6 months.
- mmm Bone marrow biopsy and aspirate must be performed within approximately 3 months prior to Day 1 of Cycle 1.
- nn For patients with bone marrow involvement at screening, a repeat assessment will be performed at the EOI, during maintenance, or at the EOM whenever there is radiologic evidence of a complete response or if clinically indicated (e.g., if there is clinical suspicion of progressive disease in the bone marrow with no radiologic evidence of progression). Additional bone marrow assessments may be performed at the discretion of the investigator.

**Appendix 1**  
**Schedule of Activities for Patients with Follicular Lymphoma:**  
**Dose-Escalation and Expansion Phases (cont.)**

**Study Treatment Administration: Dose Escalation before the Bridging Cohorts (Regimen A)**

Study Treatment	Induction (Six 28-Day Cycles)								Maintenance Every 2 Months a		
	Cycle 1 (± 1 day)					Cycles 2–6 (± 2 days)					
	Day 1	Day 5	Day 8	Day 10	Day 15	Day 1	Day 5	Day 10	Day 1	Day 5	Day 10
Obinutuzumab b (1000 mg IV)	x		x		x	x			x		
Idasanutlin b (PO QD)	Days 1–5					Days 1–5			TBD c		
Venetoclax b (PO QD)	Days 1–5 or Days 1–10 d					Days 1–5 or Days 1–10 d			TBD c		

IV = intravenous; PD = pharmacodynamic; PK = pharmacokinetic; PO = by mouth; QD = once a day; TBD = to be determined.

a Total duration of maintenance is 24 months for obinutuzumab and 6 months for idasanutlin and venetoclax.

b Refer to Section 4.3.2 for instructions on study treatment administration.

c Regimen will be defined based on available safety, tolerability, PK, and PD data.

d Regimen is defined according to the dose-escalation plan (see Section 3.1.2).

**Appendix 1**  
**Schedule of Activities for Patients with Follicular Lymphoma:**  
**Dose-Escalation and Expansion Phases (cont.)**

**Study Treatment Administration: Dose Escalation for the Bridging Cohorts (Regimen B)**

Study Treatment	Induction (Six 28-Day Cycles)								Maintenance Every 2 Months a		
	Cycle 1 (±1 day)					Cycles 2–6 (±2 days)					
	Day 1	Day 5	Day 8	Day 10	Day 15	Day 1	Day 5	Day 10	Day 1	Day 5	Day 10
Obinutuzumab b (1000 mg IV)	x		x		x	x			x		
Idasanutlin b (PO QD)						Days 1–5			TBD c		
Venetoclax b (PO QD)						Days 1–5 or Days 1–10 d			TBD c		

IV = intravenous; PD = pharmacodynamic; PK = pharmacokinetic; PO = by mouth; QD = once a day; TBD = to be determined.

a Total duration of maintenance is 24 months for obinutuzumab and 6 months for idasanutlin and venetoclax.

b Refer to Section 4.3.2 for instructions on study treatment administration.

c Regimen will be defined based on available safety, tolerability, PK, and PD data.

d Regimen is defined according to the dose-escalation plan (see Section 3.1.2).

**Appendix 1**  
**Schedule of Activities for Patients with Follicular Lymphoma:**  
**Dose-Escalation and Expansion Phases (cont.)**

**Study Treatment Administration: Expansion Phase (Regimen A or Regimen B as defined after the escalation phase)**

Study Treatment	Induction (Six 28-Day Cycles)								Maintenance Every 2 Months a		
	Cycle 1 ( $\pm 1$ day)					Cycles 2–6 ( $\pm 2$ days)					
	Day 1	Day 5	Day 8	Day 10	Day 15	Day 1	Day 5	Day 10	Day 1	Day 5	Day 10
Obinutuzumab b (1000 mg IV)	x		x		x	x			x		
Idasanutlin b, c (PO QD)	Days 1–5					Days 1–5			TBD d		
Venetoclax b, c (PO QD)	Days 1–5 or Days 1–10 e					Days 1–5 or Days 1–10 e			TBD d		

IV=intravenous; PD=pharmacodynamic; PK=pharmacokinetic; PO=by mouth; QD=once a day; TBD=to be determined.

a Total duration of maintenance is 24 months for obinutuzumab and 6 months for idasanutlin and venetoclax.

b Refer to Section 4.3.2 for instructions on study treatment administration.

c May only be given in Cycles 2–6 if this regimen is chosen.

d Regimen will be defined based on available safety, tolerability, PK, and PD data.

e Regimen is defined according to the dose-escalation plan (see Section 3.1.2).

**Appendix 2**  
**Schedule of Activities for Patients with Diffuse Large B-Cell Lymphoma:**  
**Dose-Escalation and Expansion Phases**

Assessment/Procedure	Screening a		Induction (Six 28-Day Cycles)								EOI	Consol- idation (6 Mo) d	EOC b	Post-Tx Follow-Up Period (Q3M) e	Survival Follow-Up Period (Q3M) e
	Days –28 to –1	Days –14 to –1	Cycle 1 (±1 day)				Cycle 2 (±2 days)		Cycles 3–6 (±2 days)		After Last Induction Dose c		35 Days after Last Dose		
			D 1	D 5	D 8	D 15	D 1	D 15	D 1	D 15					
Informed consent(s) f	x														
Demographic data	x														
Medical history	x														
ECOG performance status	x														
Vital signs g	x		x		x	x	x			x		x h	x i	x	
Height	x														
Weight and body surface area	x														
Triplicate 12-Lead ECG	x		x j	x j						x j		x	x j	x	
MUGA or ECHO	x k									x k		x k	x k		
Complete physical examination l, m	x														
Targeted physical examination m, n							Day 1, Cycles 2 and 4				x	x i	x	x	
Ann Arbor, IPI	x														
B symptoms o	x														

**Appendix 2**  
**Schedule of Activities for Patients with Diffuse Large B-Cell Lymphoma:**  
**Dose-Escalation and Expansion Phases (cont.)**

Assessment/Procedure	Screening a		Induction (Six 28-Day Cycles)								EOI	Consolidation (6 Mo) d	EOC b	Post-Tx Follow-Up Period (Q3M) e	Survival Follow-Up Period (Q3M) e
	Days –28 to –1	Days –14 to –1	Cycle 1 (±1 day)				Cycle 2 (±2 days)		Cycles 3–6 (±2 days)		After Last Induction Dose c		35 Days after Last Dose		
			D 1	D 5	D 8	D 15	D 1	D 15	D 1	D 15					
β 2 microglobulin			x												
Hematology p		x	x q,r		x r	x r	x r	x	x r	x	x h	x i	x		
Serum chemistry s		x	x q,r		x r	x r,t	x r	x t	x r	x t	x h	x i	x		
Coagulation (INR, aPTT [or PTT], and PT)		x													
Pregnancy test u		x									x h		x		
Hepatitis B and C, testing v	x														
Quantitative IgA, IgG, and IgM			x								x	x w	x	x x	
PK sample for obinutuzumab			x y												
PK sample for rituximab			x y												
PK sample for idasanutlin			x y												
PK sample for venetoclax			x y												
Exploratory biomarker sample			x y												
Blood for MRD z			x r				x				x	x w	x		

**Appendix 2**  
**Schedule of Activities for Patients with Diffuse Large B-Cell Lymphoma:**  
**Dose-Escalation and Expansion Phases (cont.)**

Assessment/Procedure	Screening a		Induction (Six 28-Day Cycles)								EOI	Consol- idation (6 Mo) d	EOC b		Post-Tx Follow-Up Period (Q3M) e	Survial Follow-Up Period (Q3M) e
	Days –28 to –1	Days –14 to –1	Cycle 1 (±1 day)				Cycle 2 (±2 days)		Cycles 3–6 (±2 days)		After Last Induction Dose c		35 Days after Last Dose			
			D 1	D 5	D 8	D 15	D 1	D 15	D 1	D 15						
Blood for lymphocyte immunophenotyping aa			x r			x r	x r			x r		x	x w	x	x x	
Optional serum for RBR bb			x	x												
Tumor tissue specimen (remaining tissue may be used for optional RBR specimen) cc	x cc		x dd													
Concomitant medications			To be recorded continually until end of treatment													
Adverse events ee			To be assessed continually ee													
PET-CT scan	x ff											x gg		x oo		
CT scan hh	x hh							x ii				x gg	x jj	x kk	x ll	
Bone marrow biopsy and aspirate	x mm											x gg, nn	x nn	x kk, nn		
New anti-lymphoma treatment															x	x
Survival follow-up																x

## Appendix 2

### Schedule of Activities for Patients with Diffuse Large B-Cell Lymphoma: Dose-Escalation and Expansion Phases (cont.)

BSA=body surface area; CT=computed tomography; D=day; DLBCL=diffuse large B-cell lymphoma; ECG=electrocardiogram; ECHO=echocardiogram; eCRF=electronic Case Report Form; ECOG=Eastern Cooperative Oncology Group; EOI=end of induction; EOC=end of consolidation; IPI=International Prognostic Index; MRD=minimal residual disease; MRI=magnetic resonance imaging; MUGA=multigated acquisition; PET=positron emission tomography; PK=pharmacokinetic; Q3M=every 3 months; RBR=Roche Biosample Repository; TLS=tumor lysis syndrome; Tx=treatment.

Notes: On treatment days, all assessments should be performed prior to dosing, unless otherwise specified. Assessments shaded in gray should be performed as scheduled, but the associated data do not need to be recorded on the eCRF (except in the case of an adverse event).

- a The screening period starts with the signing of the Informed Consent Form, including the optional Informed Consent Form if appropriate. Results of standard-of-care tests or examinations performed prior to obtaining informed consent and within the defined window may be used as screening and baseline assessments; such tests do not need to be repeated for screening purposes.
- b Patients who complete consolidation treatment or discontinue consolidation treatment prematurely will undergo assessments at the EOC.
- c EOI assessments should be performed 6–8 weeks after Day 1 of the last induction cycle. As an exception, patients who discontinue induction treatment prematurely because of an adverse event may undergo EOI assessments 4–8 weeks after their last dose of study treatment.
- d Consolidation treatment should start 8 weeks ( $\pm$  1 week) after Day 1 of the final cycle of induction and will continue until disease progression or unacceptable toxicity for up to 6 months.
- e Patients who complete treatment or discontinue treatment for reasons other than disease progression will undergo assessments every 3 months during the post-treatment follow-up period, which will continue until disease progression, the start of new anti-lymphoma treatment, or the end of the study, whichever occurs first. The first post-treatment follow-up visit is 3 months after the EOI visit for patients who do not receive maintenance treatment and 3 months after the last dose for patients who receive maintenance treatment. Patients who experience disease progression or start another anti-lymphoma treatment will be evaluated for survival status and new anti-lymphoma treatment every 3 months during the survival follow-up period, which will continue until the end of the study. The end of the study is defined as the time when all enrolled FL patients have completed or discontinued study treatment and all enrolled DLBCL patients have been followed for at least 1 year after they have completed or discontinued study treatment.
- f Informed consent must be documented before any study-specific screening procedure is performed.
- g Vital signs include respiratory rate, pulse rate, body temperature, and systolic and diastolic blood pressures while the patient is in a seated position. For obinutuzumab infusions: For the first cycle and for patients who experience an infusion-related reaction, vital signs will be measured prior to the infusion, every 15 ( $\pm$ 5) minutes for the first 90 minutes of the infusion, and then every 30 ( $\pm$ 10) minutes until 1 hour after completion of the infusion. For the second and subsequent cycles, vital signs will be measured every 30 minutes during the infusion, except for patients who had experienced an infusion-related reaction during a prior infusion. For rituximab infusions: Vital sign monitoring during infusion should be determined as per local label.

## Appendix 2

### Schedule of Activities for Patients with Diffuse Large B-Cell Lymphoma: Dose-Escalation and Expansion Phases (cont.)

- h Perform only for patients who will not be receiving consolidation treatment.
- i Vital signs will be measured, a targeted physical examination will be performed, and hematology and serum chemistry will be assessed during consolidation every 2 weeks during the first month, every month until EOC.
- j All ECGs should be performed within 2 hours prior to idasanutlin administration and either 6 hours after idasanutlin administration or immediately after obinutuzumab/rituximab administration, whichever occurs later. ECGs will be performed in triplicate on Days 1 and 5 of Cycles 1 and 4 in the induction phase. However, on Day 5 of Cycles 1 and 4 in the induction phase, the postdose ECG should be performed only if the patient is still at the clinic.
- k Perform MUGA or echocardiogram at screening (Day –28 to Day –1), on Day 4, Cycle 4, at the EOI, the EOC, and as clinically indicated.
- l Includes evaluation of the head, eyes, ears, nose, and throat and the cardiovascular, dermatological, musculoskeletal, respiratory, gastrointestinal, genitourinary, and neurological systems. Record abnormalities observed at baseline on the General Medical History and Baseline Conditions eCRF.
- m As part of tumor assessment, the physical examination should include evaluation for the presence of enlarged nodes, palpable hepatomegaly, and splenomegaly. This information will be recorded on the appropriate Tumor Assessment eCRF.
- n Includes systems of primary relevance (e.g., cardiovascular and respiratory systems), systems associated with symptoms (newly emergent or monitored from baseline), and areas associated with tumor assessment (lymph nodes, liver, spleen, and any other areas identified at baseline). Record new or worsened clinically significant abnormalities on the Adverse Event eCRF.
- o Unexplained fever > 38°C, night sweats, and unexplained weight loss > 10% of body weight over 6 months.
- p Includes hemoglobin, hematocrit, platelet count, RBC count, WBC count, and percent or absolute WBC differential count (neutrophils, eosinophils, basophils, monocytes, lymphocytes, other cells).
- q Screening laboratory assessments may be used for Day 1 of Cycle 1 if performed within 24 hours prior to Day 1 of Cycle 1. Additional hematology and chemistry samples must be drawn 0–4 hours pre-dose and 8 and 24 hours post-dose on Day 1 of Cycle 1 to monitor for TLS. Note that the 24-hour post-dose sample will be obtained on Day 2 of Cycle 1.
- r Perform hematology and chemistry tests within 72 hours prior to Day 1 of each cycle and within 24 hours prior to Days 8 and 15 of Cycle 1. Samples for exploratory biomarker research should be collected at the same time as hematology and serum chemistry samples.
- s Includes sodium, potassium, glucose, BUN or urea, creatinine, calculated creatinine clearance, calcium, total bilirubin, direct bilirubin, total protein, albumin, ALT, AST, alkaline phosphatase, amylase, lipase, LDH, and uric acid.
- t Perform only for patients treated with obinutuzumab.
- u All women who are not postmenopausal ( $\geq 12$  months of non-therapy-induced amenorrhea) or surgically sterile will have a serum pregnancy test at screening within 7 days prior to Day 1 of Cycle 1. Because of the suspected effect of idasanutlin or venetoclax on embryo–fetal development, monthly pregnancy testing is strongly recommended for women of childbearing potential.
- v Includes hepatitis B surface antigen, total hepatitis B core antibody, and hepatitis C virus antibody.
- w Perform at the same time as tumor assessments at 3 months after initiation of consolidation treatment.

## Appendix 2

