### 3.1.2.1 Definition of Dose-Limiting Toxicity

In this study, a DLT is defined as at least one of the following events occurring during the first two cycles of treatment and assessed by the investigator as clearly not related to the patient's underlying disease:

- Any Grade 5 adverse event unless unequivocally due to the underlying malignancy or extraneous causes
- Adverse event of any grade that leads to a delay of more than 14 days in the start of the next treatment cycle
- Hematologic adverse events that meet any of the following criteria:
  - Grade 3 or 4 neutropenia in the presence of sustained fever of  $>38^{\circ}\text{C}$  (lasting for  $>5$  days) or a documented infection
  - Grade 4 neutropenia lasting for  $>7$  days *despite adequate supportive care measures. G-CSF may be used to treat Grade  $\geq 3$  neutropenia but should not be used as prophylaxis in the DLT period.*
  - Grade 3 or 4 thrombocytopenia if associated with grade  $\geq 3$  bleeding
  - Grade 4 thrombocytopenia lasting for  $>7$  days
- Grade 3 or 4 non-hematologic adverse event, with the following exceptions:
  - Grade 3 or 4 IRRs
    - Note that IRRs are not dose-dependent events. They may occur even after a small amount of drug has been administered.
  - Grade 3 laboratory TLS without manifestations of clinical TLS (see [Appendix 5](#) for the Howard-based criteria for clinical and laboratory TLS)
  - Grade 3 AST or ALT increase lasting  $<7$  days
  - Grade 3 diarrhea that responds to adequate therapy within 48 hours

- Grade 3 nausea or vomiting that occurs in the absence of premedication and responds to adequate therapy within 72 hours
- Grade  $\leq 3$  fatigue, asthenia, anorexia, or constipation that resolves to Grade  $\leq 2$  in  $\leq 7$  days
- Any increase in hepatic transaminase  $> 3 \times$  baseline AND an increase in direct bilirubin  $> 2 \times$  ULN, WITHOUT any findings of cholestasis or jaundice or signs of hepatic dysfunction AND in the absence of other contributory factors (e.g., worsening of metastatic disease or concomitant exposure to known hepatotoxic agent or of a documented infectious etiology) is suggestive of potential drug induced liver injury (DILI) (according to Hy's Law) and will be considered a DLT.

Other toxicities that are considered clinically relevant and related to study treatment as determined by the investigator and the Medical Monitor may also be considered DLTs.

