### **Combination of Rituximab, Idasanutlin, and Venetoclax in Patients with DLBCL in the Bridging Cohorts**

Following the identification of the MTDs for idasanutlin and venetoclax in combination with obinutuzumab, *or following Sponsor decision based on clinical judgment*, a bridging cohort of patients with DLBCL will be opened to *repeat the last dose tested* in combination with rituximab instead of obinutuzumab (375 mg/m^2 on Day 1 of each cycle; see [Figure 4](#) and [Table 1](#)).

If safety and tolerability allow, idasanutlin and venetoclax dose escalations may be explored in combination with rituximab in patients with DLBCL until identification of new MTDs (see [Figure 4](#)).

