### **5.1.3 Risks Associated with Idasanutlin**

Information related to idasanutlin-associated risks is based mainly on review of data from Phase I experience in patients with solid tumors and AML (Studies NP27872, NP28902, and NP28679, respectively) as described in the Idasanutlin Investigator's Brochure. In Study NP27872 and NP28902, 160 patients with advanced malignancies (excluding leukemia) have received idasanutlin in the Phase I, entry-into-human, dose-escalation study NP27872 (99 patients) and in the Phase I DDI and relative bioavailability study NP28902 (61 patients). Study BH29812 (idasanutlin plus obinutuzumab in R/R FL and DLBCL) had enrolled 1 patient as of 1 May 2016.

Many of the toxicities experienced by patients with solid tumors appear to be manageable with appropriate prophylaxis, supportive therapies, and/or reversible with discontinuation of idasanutlin. Identified risks include GI disorders (diarrhea, nausea, and vomiting), myelosuppression (thrombocytopenia, neutropenia, and anemia), TLS, infectious complications, and electrolyte abnormalities. Potential risks include coagulation abnormalities and liver function test abnormalities.

Please refer to the current version of the Idasanutlin Investigator's Brochure for additional information on the identified and potential risks.

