#### **5.1.3.5 Electrolyte Disorders**

Electrolyte disorders (hypercalcaemia, hyperkalaemia, hyponatraemia, hypocalcaemia, hypokalaemia, hypomagnesaemia, hyponatremia, hyperphosphataemia, and hypophosphataemia) were commonly observed in patients treated with idasanutlin. In addition to institutional guidelines, electrolytes should be monitored during the treatment phase. Electrolyte disorders should be treated according to institutional guidelines.

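### Day 15 chemistry is dropped for rituximab patients only, so chemistry-based DLTs have fewer scheduled chances of detection in the rituximab bridging cohorts (5 versus 7 samples)

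*Protocol*

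**What the plan says.** Protocol Appendix 2 sets the laboratory schedule for DLBCL patients. Its serum chemistry row marks Cycle 1 Days 1, 8 and 15, and Days 1 and 15 of Cycles 2 to 6. Every Day 15 cell carries footnote t: "Perform only for patients treated with obinutuzumab". The hematology row marks the same days without footnote t, so rituximab patients still have blood drawn on Day 15.

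The timing rules are common to both antibodies:
- Footnote r: "Perform hematology and chemistry tests within 72 hours prior to Day 1 of each cycle".
- Table note: "On treatment days, all assessments should be performed prior to dosing, unless otherwise specified". The Cycle 2 Day 1 sample therefore precedes Cycle 2 dosing.
- Footnote q: "Additional hematology and chemistry samples must be drawn 0–4 hours pre-dose and 8 and 24 hours post-dose on Day 1 of Cycle 1".

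The DLT definition in Section 3.1.2.1 covers Cycles 1 and 2 and does not distinguish between antibodies. Grade 3 or 4 non-hematologic adverse events count, with listed exceptions, one of which is "Grade 3 AST or ALT increase lasting $<7$ days". A separate rule counts a combined rise in transaminases and direct bilirubin. In the rituximab bridging cohorts, if tolerability allows, "idasanutlin and venetoclax dose escalations may be explored in combination with rituximab in patients with DLBCL until identification of new MTDs". Section 3.1.2.3 says that a similar mCRM will support this.

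On idasanutlin, which both groups receive, Section 5.1.3 says "Potential risks include coagulation abnormalities and liver function test abnormalities", and Section 5.1.3.5 says "electrolytes should be monitored during the treatment phase".

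**The concern.** The DLT definition, the two oral drugs and the type of escalation model are the same for both antibodies, but the chemistry schedule is not. A DLT that shows only in a chemistry panel (raised AST/ALT, the transaminase-plus-bilirubin rule, or a Grade 3 or 4 electrolyte or other chemistry adverse event) has fewer scheduled chances of being seen with rituximab.

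The documents give no reason for footnote t. Infusion days do not supply one. Obinutuzumab is given on Day 15 only in Cycle 1, yet the footnote also marks Day 15 of Cycles 2 to 6. Rituximab patients also keep Day 8 chemistry in Cycle 1, although rituximab is given only on Day 1. In consolidation, footnote i of the same appendix asks for chemistry every 2 weeks in the first month regardless of antibody. That is denser than Cycle 2 with rituximab, which lies inside the DLT window.

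What is at stake is even ascertainment in the cohorts that inform the DLBCL dose. An abnormality that was never sampled cannot be recovered later.

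**Working it through.** The plan gives no figure to reproduce. The check counts scheduled samples, then illustrates what the gaps mean.

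**Scheduled chemistry after the first dose, up to the pre-Cycle 3 sample.** Inputs are the Appendix 2 row with footnotes q, r and t, and 28-day cycles, so Cycle 1, 2 and 3 Day 1 are study days 1, 29 and 57.

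| Antibody | Study days | Samples | Gaps (days) |
|---|---|---|---|
| Obinutuzumab | 1 (8 h), 2 (24 h), 8, 15, 29, 43, 57 | 7 | 1, 6, 7, 14, 14, 14 |
| Rituximab | 1 (8 h), 2 (24 h), 8, 29, 57 | 5 | 1, 6, 21, 28 |

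The longest gap is 14 days with obinutuzumab and 28 with rituximab. For hematology the two schedules are identical.

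**Illustration for Cycle 2.** Assumptions, none of them from the documents: an abnormality lasts L days, starts uniformly within the gap, and prompts no unscheduled draw. The chance that scheduled samples miss it is (gap − L)/gap.
- L = 7 (the shortest Grade 3 AST/ALT rise outside the exemption): rituximab (28 − 7)/28 = 75%; obinutuzumab (14 − 7)/14 = 50%.
- L = 14: rituximab (28 − 14)/28 = 50%; obinutuzumab (14 − 14)/14 = 0%.

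Footnote r allows the pre-Cycle 3 sample to be early. With that draw 1 to 3 days before Cycle 3 Day 1, onset is spread over 27 to 25 days:
- L = 7, detected: rituximab 7/27 to 7/25 = 26% to 28%; obinutuzumab 14/27 to 14/25 = 52% to 56%.
- L = 14, detected: rituximab 14/27 to 14/25 = 52% to 56%; obinutuzumab 100%.

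Uniform onset may flatter the rituximab schedule. Idasanutlin is given on Days 1 to 5. An abnormality starting on Cycle 2 Day 5 (study day 33) must last 43 − 33 = 10 days to reach a Day 15 draw, but 54 − 33 = 21 to 57 − 33 = 24 days to reach the pre-Cycle 3 draw.

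**Rough effect on a DLT rate.** Appendix 13 (idasanutlin alone, mainly solid tumors) prints 1% for raised ALT, 3% for hypokalemia and 1% for hyponatremia. Its column headers and percentages do not fully agree, and these are not DLT rates, so they serve only for order of magnitude. I leave out its hypophosphatemia entry because phosphate is not in the footnote s panel. Assume a true rate of chemistry-only DLTs between 1% and 1 + 3 + 1 = 5%, all arising in Cycle 2. The extra share missed with rituximab is 75 − 50 = 25 points (L = 7) to 50 − 0 = 50 points (L = 14). The observed DLT rate then falls by between 1% × 0.25 = 0.25 and 5% × 0.50 = 2.5 percentage points, against a target interval of 16% to 33%.

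**The case against.** The strongest case on the other side has five parts.

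- **Hematologic toxicity dominates.** Earlier DLTs with daily-for-5-days idasanutlin were cytopenias, febrile neutropenia and diarrhea, and with venetoclax in NHL they were neutropenia and febrile neutropenia (Sections 1.3.2 and 1.4.2.1). Their scheduled detection does not differ between antibodies. This stands, and it limits the point to chemistry-based DLTs.
- **A laboratory value is not automatically a DLT.** Section 5.3.5.5 requires symptoms, a treatment change, an intervention or clinical significance before it counts as an adverse event. A silent, self-resolving abnormality is the type least sure to qualify. One Day 15 draw also cannot show that a Grade 3 AST/ALT rise lasted 7 days. This stands, although an abnormal draw is what would prompt the repeat tests.
- **Other monitoring exists.** Electrolytes are to be followed during treatment, diarrhea triggers electrolyte checks, and the early TLS samples apply to both antibodies. This stands, and it makes the illustrated miss rates upper values. None of it schedules liver tests on Day 15.
- **Rituximab is expected to be milder.** Section 3.3.2.1 expects less pronounced overlapping toxicity with idasanutlin. It uses this to explain why no alternative rituximab regimen is explored, not why chemistry is dropped.
- **The model has a brake.** The bridging cohort first repeats the last dose tested, and Section 3.1.2.3 puts clinical judgment above the model.

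A reader might infer more than the documents support: that Cycle 2 has no chemistry at all (a pre-dose Day 1 sample is scheduled for everyone), that laboratory DLTs in general are under-detected (hematology is unchanged), or that the mCRM will select a higher MTD (the documents give no detection rates, and no shift in the model has been shown). Lack of comparability of DLT rates between antibodies affects no planned analysis.

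**Conclusion.** The point holds in limited form. With rituximab there are 5 rather than 7 scheduled post-dose chemistry samples through pre-Cycle 3, with gaps of about 21 and 28 days, under the same DLT definition. The direction of any bias is known: fewer looks can leave the observed count of chemistry-based DLTs the same or lower, never higher. Its size is not known. Under the assumptions above it is of the order of 0.25 to 2.5 percentage points on a DLT rate, and unscheduled testing would reduce it.

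The consequence for dose finding concerns the bridging cohorts. DLTs do not drive decisions in the expansion phase, so Day 15 of Cycles 3 to 6 and the roughly 40 DLBCL expansion patients lie outside this argument. This is a cheap improvement to ascertainment, not a flaw that invalidates the escalation.

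**What to change.** Remove footnote t from the Cycle 1 Day 15 and Cycle 2 Day 15 serum chemistry cells of Appendix 2, so that chemistry is drawn with the hematology sample already scheduled in rituximab patients. Both antibodies would then have 7 post-dose samples through pre-Cycle 3 and a longest gap of 14 days. Make the change before rituximab DLT data enter the model.

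In the same amendment, reconcile the table with footnote r and Section 5.1.8. Both refer to laboratory values before Cycle 1 Day 15 without an antibody restriction, whereas the table cell adds one. They also give different lead times before Day 1 (72 hours in footnote r, 48 hours in Section 5.1.8).

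The cost is a schedule-of-activities amendment and one extra chemistry tube at each of two existing draws, with no new visit. Extending the change to Cycles 3 to 6 and the expansion phase is optional and would need a reason other than DLT ascertainment. If the sponsor keeps footnote t, the protocol should state why.
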